access data. The study research assistant will use a login name and password to gain access to the software in order to administer it to a participant, but they will have no ability to access the saved data. The database, data structure, and data quality will be routinely reviewed by the contact Principal Investigator (PI), [name]. [name] will work closely to plan analyses for various purposes, including for hypothesis testing and manuscript development and reports. Data quality will be examined before statistical analyses are conducted, including examination of missing data, assessment of distributional assumptions, and identification of outliers. In addition to data quality, the comparability between intervention and control groups will be carefully examined, including baseline balance and differential attritions at all waves of follow-up. While differences are not expected from the randomized design, it is prudent to plan for this contingency so that sufficient follow-up data and appropriate statistical methods can be used for intent-to-treat analyses. The psychometric properties of instruments will also be examined, as will the patterns of missing data.

Training on human subjects and data safety and monitoring. All staff will participate in the National Institutes of Health (NIH) required trainings for the conduct of studies that involve human subjects, and any future study staff will do so upon hiring. Training for all staff includes (but is not limited to) Human Subjects, Informed Consent, Good Clinical Practice, Quality Management, Confidentiality, and Reporting of Adverse Events. If any study staff discovers any untreated condition (e.g., onset of physical or mental health condition), they will refer participants to appropriate treatment immediately.

Data Safety and Monitoring Committee. This study will also have a data safety monitoring committee (DSMC) which will meet yearly *via Zoom*. The DSMC will consist of individuals who are not otherwise associated with the study. The DSMC will meet at least yearly to review study progress, adequacy of randomization, and, at their discretion, adverse events or differential outcomes. For randomization, we will tabulate the number of individuals who have been randomly assigned to each condition at each of the DSMC meetings. Before the DSMC meeting, relevant information will be tabulated to report to the DSMC, and after the meeting, staff of the management core will collect minutes and distribute to the board for sign-off. The final report will be submitted to the Institutional Review Board (IRB) on an annual basis.

Procedures for Monitoring Adverse Events. Per guidance provided by the Office of Human Subjects Research at the NIH, an adverse event (AE) is any unfavorable and unintended diagnosis, symptom, sign (including an abnormal laboratory finding), syndrome, or disease which either occurs during the study, having been absent at baseline, or, if present at baseline, appears to worsen. A serious adverse event (SAE) is defined as an untoward medical occurrence that: 1) results in death, 2) is life threatening, 3) requires (or prolongs) hospitalization, 4) causes persistent or significant disability/incapacity, 5) results in congenital anomalies or birth defects, or 6) is another condition which in the judgment of the investigators represents significant hazards.

Possible AEs that are anticipated include the need to violate the confidentiality of the participants. All study personnel will be trained regarding the limits of confidentiality. The training will include reviewing possible scenarios and knowledge of key questions to assess risk. We will train staff to err on the side of caution and to contact the clinical supervisor as needed. Coordinators will be available on site or via phone after hours should staff need consult regarding an emergency. In this situation, we will train all staff to immediately contact clinical supervisors, and under the guidance and direction of clinical supervisors, study staff will be trained when to either contact police to ensure the safety of participants.

Possible AEs that are unanticipated will be brought to the attention of the Coordinators and reported immediately to both site IRBs. All study staff will be trained to recognize and report AEs and SAEs. Possible AEs will immediately (within 24 hours) be brought to the attention of the Lead at each site by study staff who identify the event. The Site Lead will report the AEs and SAEs to the IRB in writing as soon as possible, but within 7 calendar days for death or life-threatening events and within 15 calendar days for all other AEs or SAEs. The IRBs will determine whether it is appropriate to stop the study protocol temporarily or will provide suggestions/modifications to the study procedures as necessary. Possible modifications include adding these possible adverse events to the consent form and re-consenting all study participants. The PIs will be responsible for monitoring participant safety on a monthly basis at regularly scheduled research meetings. They will keep a written log of all events and ensure that the IRB is contacted immediately. They will also keep a log of the outcome of IRB decisions regarding AEs and apprise the research team of any changes that need to occur because of IRB decisions.

STATISTICAL DESIGN AND POWER

Sample Size and Power. The goal of this pilot study is to estimate the smoking cessation rates in each arm to obtain an effect size for future larger studies. To conduct a hypothesis test for the comparison of cessation rates between the two intervention arms, it requires a minimal sample size of 199 per group (total 398) for at least 80% power. This calculation was based on a 2-sided test with the type I error of 0.05, and assuming a 20% cessation rate in the *Sense2Quit* App group (intervention) and a 10% cessation rate in the control arm. The 10% difference would be equivalent to a medium effect size (Cohen's $d=0.45$). In this pilot study, we propose a total sample of 60 (30 per group). Therefore, this study is not powered to detect a significant difference between arms. Instead, we estimated the minimal sample size for the estimation of cessation rates in each arm with acceptable reliability. For the sample size (30 per group), this study will have at least 80% probability that the standard error of the cessation rate estimates $\leq 7\%$, assuming expected cessation rates ranging from 10% to 20%. Therefore, the sample size is sufficient to provide estimation with acceptable reliability.

Statistical Design and Data Analysis: This is a pilot study to assess preliminary feasibility, acceptability, and preliminary efficacy. Descriptive statistics will be used for all analyses. The rate of quit attempts will be calculated as the proportion of smokers who attempt to quit (i.e., no smoking during a 24-hour period); 7-day point prevalence abstinence will be calculated as the proportion of smokers who are biochemically verified 7-day abstinence at a given time point; and sustained abstinence will be calculated as proportion of days of no smoking starting on the quit date among those who attempt to quit. We will provide point estimates and corresponding confidence intervals of these measures for each arm. Because of small sample sizes, we will obtain Clopper-Pearson exact confidence intervals based on the binomial distribution. Given the small sample size, the purpose of the arms is simply to monitor for unexpected, gross differences between the two groups. To determine acceptability, we will ask participants in both arms how useful each of the intervention components were (1 = *Not at all useful* to 7 = *Extremely useful*) and whether they would recommend the program to a friend (1 = *Definitely would not recommend* to 7 = *Definitely would recommend*). For the intervention to be deemed acceptable, the mean level for each of these measures would have to be 5 or higher. The efficacy of the intervention will be based on saliva-confirmed 7-day point prevalence abstinence at the follow-up survey. Lost-to-follow-up participants will be included as smokers.

DISSEMINATION PLAN

Tools developed and evaluated during this project have the potential to extend the impact and reach of tobacco cessation for all smokers but specifically for persons living with HIV (PLWH) who smoke. Per the RFA, this study was designed for dissemination (e.g., feasibility/acceptability of the intervention for PLWH) and suitable for the intended context.

Therefore, a multi-faceted dissemination plan targeting various stakeholders is proposed. We will disseminate our findings to technology-oriented and clinical management-oriented audiences. For technology audiences, we will provide enough detail to enable the *Sense2Quit App* to be constructed and used within an appropriate context.

We propose the following dissemination strategies:

1. Members of the research team will present the results of this study in several different venues targeting different audiences, including conferences such as the American Public Health Association and Society for Behavioral Medicine.
2. We will seek out appropriate organizations that are influential in HIV and tobacco cessation public health practice (e.g., International AIDS Society, Society for Research on Nicotine and Tobacco). We will provide these organizations with an executive summary, press releases, and/or published papers and present study findings at local community-based organizations.
3. We plan to publish our results in appropriate high-impact, peer-reviewed academic journals such as the *American Journal of Public Health, AIDS and Behavior*, and *Nicotine and Tobacco Research*.
4. We will work with our local community-based organizations (e.g., Alliance for Positive Change, Gay Men's Health Crisis, LGBT Center) to disseminate our study findings to the community.

All informed consent documents for this clinical trial will include a specific statement relating to posting of clinical trial information at ClinicalTrials.gov. We will register this study with ClinicalTrials.gov. Finally, the recipient institution (Columbia University) has an internal policy in place to ensure that clinical trials registration and results reporting occur in compliance with policy requirements. Specifically, the Human Research Protection Office and Institutional Review Boards have policies to ensure that clinical trials registration reporting occurs in compliance with policy requirements.

Specifically, the Human Research Protections Office and Institutional Review Boards have policies to ensure that clinical trials registration reporting occurs in compliance with policy requirements.

Presentations at national scientific meetings. It is expected that we will present our findings at HIV, tobacco-cessation, behavioral health, informatics, and engineering related scientific meetings. We will also disseminate the findings through relevant newsletters and websites of related interest groups.

We will also make de-identified data from our study available. Researchers interested in replicating our methods and study findings will have full access to the study protocol, analytic methods, and codebook of qualitative data analysis. We will deliver versions of our protocol with our first 12-month progress report. We will deliver our final protocol, codebook documents, and instructions regarding how other researchers can access our study documents to the NIH within 12 months of the end of the funding period. In addition to the documents mentioned above, de-identified transcripts from our in-depth interviews will be available at the conclusion of the study. The de-identified transcripts will be archived on the secure network server provided to the Contact PI at Columbia University Irving Medical Center. A Data Use Agreement will be implemented for other researchers interested in using our data for replication of research findings or for additional areas of research. We will request that outside investigators discuss their manuscript ideas with the PIs before proceeding. Furthermore, we will request that manuscripts using data from our project be approved by the PIs prior to submission for publication. Members of this project team may contribute as co-authors when data from this study are used. We will request that manuscripts, abstracts, presentations, and chapters developed by other investigators credit this study and credit NIH as the funding source for the data. This process will allow for a central repository and access point for all papers, abstracts, posters, and presentations by any individual or organization using our data.

Our plan for sharing research data and resources is designed to assure that data generated in this project are made as widely and freely available as possible while safeguarding the privacy of participants and protecting confidential and proprietary information.

REFERENCES

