Inclusion criteria: For Aim 1, (1) PLWH; (2) ≥ 18 years of age; (3) current or former smoker (where smoking is defined as ≥ 5 cigarettes a day for the past 30 days, past smoker is defined as having at one point smoked a minimum of ≥ 5 cigarettes per day for a period of at least 30 days) and (4) understand and read English; Aims 2 and 3 follow the same inclusion criteria with the added criteria that (1) PLWH will be confirmed through medical records or pill bottles for ART medications; (2) only current smokers are eligible (where smoking is defined as ≥ 5 cigarettes a day for the past 30 days); (3) own an Android smartphone (if they do not have a phone compatible with the app, they will be provided with one to use during the study); (4) not pregnant or breastfeeding (due to contraindications for Nicotine Replacement Therapy [NRT]); (5) permanent contact information; (6) interested in quitting smoking within 30 days; and (7) blows ≥ 5 CO into a breath analyzer at baseline. For Aim 4) participants will be PWH who smoke cigarettes and will either be 1) enrolled participants at their 12-week follow-up visit; 2) participants who are initially eligible for the study after completing the screener but do not qualify based on eCO levels; or 3) participants who already finished Aim 2 (and 3, if applicable).

Exclusion criteria. For Aim 1, participants will be excluded if they do not meet the defined inclusion criteria. For Aims 2 and 3, the exclusion criteria will be (1) use tobacco products other than cigarettes (i.e., cigars, piped tobacco, chew, snuff); (2) planning to move within 6 months of enrollment; (3) alcohol dependence measured through the AUDIT-C⁶⁰; (4) positive history of a medical condition that precludes nicotine patch use; (5) current use of NRT or other smoking cessation medications (e.g., Chantix or Zyban); (6) current enrollment in another smoking cessation program; and (7) household member is also participating in the Sense2Quit study (due to study contamination). For Aim 4, participants will be excluded if they fail to meet the inclusion criteria.

Inclusion of Individuals

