use the app for the duration of the study period. Two days after baseline, a study team member will reach out to the intervention arm study participant to see if they have any questions or issues with the *Sense2Quit App* and/or watch. The study coordinator will be able to access smoking behaviors and subject information through the online dashboard. The study coordinator will also reach out to participants in both arms once a week through phone call to check-in about their quitting process. At 4 and 12 weeks after baseline, participants in both study arms will attend a follow-up visit at the study site. Participants will report a 7-day point prevalence abstinence of smoking cigarettes⁷⁶ and provide a breath sample using Micro^{+TM basic} Smokerlyzer®. They will also be given a follow-up survey with questions asked at baseline and process questions dictated by the primary outcomes that assess usability and acceptability of *Sense2Quit* (see **Table 3**). We will use skip logic features in our study surveys to identify subjects who select certain responses indicating depression, substance abuse, and/or alcohol abuse and referral information will be presented at the end of the survey. Referral information will include contact information for the Comprehensive HIV Program (CHP) at New York- Presbyterian/Columbia University Irving Medical Center, which offers comprehensive care and services for people living with HIV. Participants completing the survey(s) on-site will be asked if they want to be escorted by staff to CHP.

Table 3. Study Measures

Construct	Measures
Demographics	Gender, age, education, income, employment, health insurance, housing, time since diagnosis with HIV, health literacy (measured by S-TOFHLA). ⁷⁵ and co-morbid conditions
Tobacco Use History	Age of initiation, current smoking, daily smoking, e-cigarette use, types of products used, history of quit attempts, prior use of quitline/telephone counseling services
Tobacco Cessation	CO lung/blood concentration, 7-day point prevalence abstinence – Timeline follow-back ^{76, 77} (confirmed with saliva cotinine); number of quit attempts; days of continuous abstinence
Illicit Substance and Alcohol Use	NIDA ASSIST ^{78, 79} , AUDIT-C ⁶⁰
Predictors of Tobacco Cessation	Fagerstrom Test for Cigarette Dependence, ⁸⁰ Readiness to quit ⁸¹
Cravings and Withdrawal	Minnesota Withdrawal Scale ⁸²
Psychosocial Factors	Depression: CESD score ⁸³ ; Anxiety: STAI score ⁸⁴ , Social support ⁸⁵

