Marker of HIV/AIDS immune status	CD4, viral load (chart review), Case Adherence Index (self-report) ⁸⁶
Follow Up Visit Only	
Pharmacotherapy Use	Nicotine replacement therapy Adherence
Intervention Quality	Health-ITUES ⁶³ ; Post-System Study Usability (PSSUQ) ⁸⁷ , Intervention ratings

Operationalization of Outcome Measures:

The primary outcome for determining preliminary efficacy will be biochemically (saliva cotinine) validated 7-day point prevalence abstinence.

Subjective Data (e.g., health status, quality of life) and system use will be obtained from subjects for the specific research purposes of this study. Follow-up visits will be completed on-site at the study location.

Carbon Monoxide Monitoring. We will be using a carbon monoxide detector to biochemically verify tobacco use. *Medical Records.* We will be reviewing patient records to assess participants' CD4 and viral loads. For participants who are not patients at CUIMC, they will be asked to bring in their most recent CD4/viral load laboratory data from their last visit to their healthcare provider.

Compensation: Eligible participants will be able to receive \$40 for completing baseline study procedures, \$50 at the 4-week follow-up study visit, and \$60 at the 12-week follow-up study visit.

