Data Analysis: This is a pilot study to assess preliminary feasibility, acceptability, and efficacy. Descriptive statistics will be used for all analyses. The rate of quit attempts will be calculated as the proportion of smokers who attempt to quit (i.e., no smoking during a 24 hours period); 7-day point prevalence abstinence will be calculated as the proportion of smokers who are biochemically verified (saliva cotinine) 7-day abstinence at a given time point; and sustained abstinence will be calculated as proportion of days of no smoking starting on the quit date among those who attempt to quit. We will provide point estimates and corresponding confidence intervals of these measures for each arm. Because of our small sample sizes, we will obtain Clopper-Pearson exact confidence intervals based on the binomial distribution. Given the small sample size, the purpose of the arms is to monitor for unexpected, gross differences between the two groups. To determine acceptability, we will ask participants in both arms how useful each of the intervention components were (1 = *Not at all useful* to 7 = *Extremely useful*) and whether they would recommend the program to a friend (1 = *Definitely would not recommend* to 7 = *Definitely would recommend*). For the intervention to be deemed acceptable, the mean level for each of these measures would have to be five or

higher. The efficacy of the intervention will be based on saliva- confirmed 7-day point prevalence abstinence at the final study visit. Lost-to-follow-up participants will be included as smokers.

NOT-OD-15-102: Consideration of Sex as a Biological Variable: In accordance with NIH guidance, we will include sex as a biological variable in the study design (enroll equal numbers of males and females), analyses, and reporting. We will report all primary and secondary outcomes separately by sex to enhance rigor and transparency of our findings in addition to including sex in all multivariate models.

AIM 3: Employ the RE-AIM framework to assess the potential scale-up of the *Sense2Quit App*.

In addition to testing the Efficacy of the *Sense2Quit App*, we will concurrently measure the four remaining RE-AIM dimensions⁸⁸ as follows:

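### Cigarette abstinence is verified only by saliva cotinine, so abstainers who use e-cigarettes or NRT can be left out of the primary-endpoint numerator

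*Combined protocol and SAP*

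**What the plan says.** **Behaviour.** Under Aim 2, Procedures, for the visits at weeks 4 and 12: "Participants will report a 7-day point prevalence abstinence of smoking cigarettes". A breath sample for CO is taken at the same visits.

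**Verifier.** Operationalization of Outcome Measures: "The primary outcome for determining preliminary efficacy will be biochemically (saliva cotinine) validated 7-day point prevalence abstinence". The Aim 2 Data Analysis section counts the "proportion of smokers who are biochemically verified (saliva cotinine) 7-day abstinence at a given time point", and judges efficacy on saliva-"confirmed 7-day point prevalence abstinence at the final study visit", which is week 12. Statistical Design and Data Analysis says only that abstinence is biochemically verified when it defines the rate, but its efficacy sentence again requires saliva confirmation. No cotinine cut-off is given.

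**Other nicotine at entry.** Exclusion (1) for Aims 2 and 3 is "use tobacco products other than cigarettes (i.e., cigars, piped tobacco, chew, snuff"). Exclusion (5) is "current use of NRT or other smoking cessation medications (e.g., Chantix or Zyban"). E-cigarettes are named in neither. Table 3 records them under tobacco use history ("current smoking, daily smoking, e-cigarette use, types of products used, history of quit attempts"), but no eligibility or outcome rule uses the item.

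**Other nicotine during the trial.** Aim 2, Procedures gives the active arm 8 weeks of combination NRT and refers controls to the Quitline, where they can obtain it. The Overview adds that gum or lozenges can be bought over the counter.

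**CO.** The Carbon Monoxide Monitoring paragraph says CO serves to verify tobacco use biochemically. No sentence says what happens when CO and cotinine disagree.

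**The concern.** The behaviour in the endpoint is smoking cigarettes; the marker that decides the endpoint is a metabolite of nicotine. That cotinine cannot tell smoked nicotine from vaped or therapeutic nicotine is general pharmacology, not something the documents state. It means that a person who has truthfully stopped cigarettes can still test positive. Only verified participants enter the numerator, so that person falls on the same side as continuing smokers.

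The Sample Size and Power sections give the pilot's goal as estimating the cessation rate in each arm, to supply an effect size for a larger trial. A rule that removes some true abstainers lowers those rates. If use of other nicotine differs by arm, it also distorts the difference. A difference by arm is plausible: the study supplies NRT to one arm only, and that arm's app sends reminders to use a nicotine substitute near trigger locations (Specific Aims) for as long as the app is used, which is the whole study period.

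**Working it through.** **1. Trace one participant through the rules.** Take someone who reports no cigarettes for 7 days at week 12 and uses an e-cigarette or NRT.
- Entry: neither exclusion names e-cigarettes, and both exclusions act at enrolment only, so later uptake of e-cigarettes or NRT is not covered.
- Self-report: meets the cigarette-abstinence definition.
- Verification: cotinine only. If it is above the cut-off, the participant is not verified.
- Numerator: not included. No rule lets a low CO reading change this.

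The same holds at week 4, because abstinence is calculated at each time point and the 8-week NRT supply is then still running.

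**2. Reproduce the plan's own figure.** Inputs from Sample Size and Power: 20% v 10%, two-sided α = 0.05, 80% power. With pooled variance under the null, mean rate 0.15:

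n = [1.960 × √(2 × 0.15 × 0.85) + 0.842 × √(0.20 × 0.80 + 0.10 × 0.90)]² / 0.10² ≈ 199 per arm.

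This matches the stated 199 and is not in dispute.

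**3. Effect of misclassification.** Let v be the share of true cigarette abstainers whose other nicotine use makes cotinine positive. The documents give no value; 0–30% is an assumption. The step also assumes that 20% and 10% are true cigarette-abstinence rates. Verified rate = true rate × (1 − v). The last column is the formula in step 2 applied to the verified rates.

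| v (both arms) | Active | Control | Difference | n per arm for 80% power |
|---|---|---|---|---|
| 0 | 20% | 10% | 10 points | 199 |
| 10% | 18% | 9% | 9 points | 226 |
| 20% | 16% | 8% | 8 points | 258 |
| 30% | 14% | 7% | 7 points | 300 |

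If only one arm is affected (extreme cases that show the direction):

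| v | Active arm only: difference | Controls only: difference |
|---|---|---|
| 10% | 18 − 10 = 8 points | 20 − 9 = 11 points |
| 20% | 16 − 10 = 6 points | 20 − 8 = 12 points |
| 30% | 14 − 10 = 4 points | 20 − 7 = 13 points |

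**4. Pilot scale.** Participants lost to follow-up stay in the denominator as smokers, so each arm has 30. One reclassified person moves a rate by 1/30 = 3.3 points: 6/30 = 20.0% (Clopper-Pearson 95% CI 7.7–38.6%) becomes 5/30 = 16.7% (5.6–34.7%). At v = 30% the expected number misclassified is 30 × 0.20 × 0.30 = 1.8 in the active arm and 30 × 0.10 × 0.30 = 0.9 in controls; at v = 0 it is none.

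**The case against.** **E-cigarettes may already be excluded.** Exclusion (1) bars other tobacco products, and Table 3 files e-cigarettes under tobacco use history, so screening staff could read them as covered. The list after *i.e.* looks closed, but the document uses that abbreviation loosely elsewhere. A reader might infer from Table 3 that e-cigarette users are expected in the trial. That does not follow: the same row records types of products used, although other tobacco is excluded, and AUDIT-C is collected although alcohol dependence on it is an exclusion. This part of the objection stands. It does not remove the problem, because an exclusion at entry cannot cover e-cigarettes taken up during a quit attempt, or NRT that the trial itself supplies or makes available.

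**Not every user would fail.** A reader might infer that anyone who vapes is counted as a smoker at week 12. The documents do not support that. Without a cut-off, no one can say which users test positive, and the explicit rule on counting people as smokers covers only loss to follow-up. For other nicotine users the result follows from the numerator definition.

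**NRT is finished by week 12.** Supply used on schedule ends at week 8, four weeks before the final visit. This limits the effect of study-supplied NRT at week 12. It does not cover week 4, late or continued use, purchased gum or lozenges, or Quitline NRT, which has no fixed timing.

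**The effect is small beside the noise.** The trial is descriptive and states that it is not powered to compare arms, and the exact interval for 6/30 spans about 31 points. This is true, but the interval does not account for a systematic shift, and the rates are the figures to be carried into the next trial.

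**Conclusion.** The verifier does not match the behaviour in the endpoint, and no rule resolves the conflict. Cigarette-abstinent participants whose e-cigarette or NRT use puts cotinine above the unstated cut-off are left out of the numerator, which lowers the verified cessation rates and may do so unequally by arm.

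The size is unknown from the documents. The fall from 10 points to as low as 7 rests on two assumptions: a share of 0–30% affected equally in both arms, and 20% v 10% being true cigarette-abstinence rates. The plan calls these only cessation rates; if they are meant as cotinine-verified rates, the multiplication by (1 − v) does not apply to them. A reader might therefore infer that the 199 per arm is wrong, or that the pilot must understate the app's effect. Neither is supported: the 199 reproduces, and unequal use can push the difference either way. This is an inexpensive improvement worth making, not a fatal flaw.

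**What to change.** In Operationalization of Outcome Measures, Aim 2 Data Analysis, and Statistical Design and Data Analysis, state one rule:
- Participants who report no cigarettes but report e-cigarette or NRT use in the past 7 days are verified by the breath CO already taken at that visit, at a pre-specified CO cut-off.
- All others are verified by saliva cotinine at a pre-specified cut-off.

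Also:
- Ask e-cigarette and NRT use with a 7-day window at weeks 4 and 12.
- Report, by arm, how many were verified by each method.
- Give the cotinine-only result for everyone as a sensitivity analysis, which requires saliva from all participants.
- Settle the rule before outcomes are classified.

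**Cost.** Protocol wording and a recall window on survey items. Baseline questions are already repeated at follow-up, and Table 3 already lists NRT adherence there. No new visit or sample type is needed.

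**Downside.** CO has a shorter look-back and can miss light smoking. The plan's own Aim 4 recruitment anticipates people who pass the smoking screener but do not qualify on CO. Self-report also selects the verifier for this subgroup, so a smoker could avoid cotinine by reporting other nicotine. The counts by method and the cotinine-only analysis make both visible.

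Adding e-cigarettes to exclusion (1) is not sufficient alone: it does nothing about later uptake or about NRT.
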